1.2 TARGET LESIONS: SPECIFICATIONS BY METHODS OF MEASUREMENTS

1.2.1 MEASUREMENT OF LESIONS

All measurements should be recorded in metric notation, using calipers if clinically assessed. All baseline evaluations should be performed as close as possible to the treatment start and never more than 4 weeks before the beginning of the treatment.

1.2.2 METHOD OF ASSESSMENT

The same method of assessment and the same technique should be used to characterize each identified and reported lesion at baseline and during study. Imaging based evaluation should always be the preferred option.

Clinical lesions: Clinical lesions will only be considered measurable when they are superficial and ≥ 10 mm diameter as assessed using calipers (e.g. skin nodules). For the case of skin lesions, documentation by color photography including a ruler to estimate the size of the lesion is suggested.

Chest X-ray: Chest CT is preferred over chest X-ray, particularly when progression is an important endpoint, since CT is more sensitive than X-ray, particularly in identifying new lesions. However, lesions on chest X-ray may be considered measurable if they are clearly defined and surrounded by aerated lung.

CT, MRI: CT is the best currently available and reproducible method to measure lesions selected for response assessment. This guideline has defined measurability of lesions on CT scan based on the assumption that CT slice thickness is 5 mm or less. When CT scans have slice thickness greater than 5 mm, the minimum size for a measurable lesion should be twice the slice thickness. MRI is also acceptable.

If prior to enrollment it is known that a patient is unable to undergo CT scans with IV contrast due to allergy or renal insufficiency, the decision as to whether a non-contrast CT or MRI (without IV contrast) will be used to evaluate the subject at baseline and during study, should be guided by the tumor type under investigation and the anatomic location of the disease. For patients who develop contraindications to contrast after baseline contrast CT is done, the decision as to whether non-contrast CT or MRI (enhanced or non-enhanced) will be performed, should also be based on the tumor type, anatomic location of the disease and should be optimized to allow for comparison to the prior studies if possible. Each case should be discussed with the radiologist to determine if substitution of these other approaches is possible and, if not, the patient should be considered not evaluable from that point forward.

Ultrasound: Ultrasound is not useful in assessment of lesion size and should not be used as a method of measurement.

Endoscopy, Laparoscopy, Tumor markers, Cytology, Histology: The utilization of these techniques for objective tumor evaluation cannot generally be advised but will be dependent on the study design.

2 TUMOR RESPONSE EVALUATION

2.1 ASSESSMENT OF OVERALL TUMOR BURDEN AND MEASURABLE DISEASE

To assess objective response or future progression, it is necessary to estimate the overall tumor burden at baseline and use this as a comparator for subsequent measurements. Measurable disease is defined by the presence of at least one measurable lesion (as detailed above in Section 1.1.1).

2.2 BASELINE DOCUMENTATION OF ‘TARGET’ AND ‘NON-TARGET’ LESIONS

When more than one measurable lesion is present at baseline, all lesions up to a maximum of five lesions total (and a maximum of two lesions per organ) representative of all involved organs should be identified as target lesions and will be recorded and measured at baseline.

This means in instances where patients have only one or two organ sites involved a maximum of two (one site) and four lesions (two sites), respectively, will be recorded. Other lesions (albeit measurable) in that organ will be recorded as non-measurable lesions (even if size is greater than 10mm by CT scan).

Target lesions should be selected on the basis of their size (lesions with the longest diameter), be representative of all involved organs, but in addition should be *reproducible in repeated measurements*. It may be the case that, on occasion, the largest lesion does not lend itself to reproducible measurement in which circumstance the next largest lesion which can be measured reproducibly should be selected.

Lymph nodes merit special mention since they are normal anatomical structures which may be visible by imaging even if not involved by tumor. As noted in Section 1.1.1, pathological nodes which are defined as measurable and may be identified as target lesions must meet the criterion of a short axis of ≥ 15 mm by CT scan. Only the short axis of these nodes will contribute to the baseline sum. The short axis of the node is the diameter normally used by radiologists to judge if a node is involved by solid tumor. Nodal size is normally reported as two dimensions in the plane in which the image is obtained (for CT scan this is almost always the axial plane; for MRI

the plane of acquisition may be axial, sagittal or coronal). The smaller of these measures is the short axis. For example, an abdominal node which is reported as being 20 mm x 30 mm has a short axis of 20 mm and qualifies as a malignant, measurable node. In this example, 20 mm should be recorded as the node measurement. All other pathological nodes (those with short axis \geq 10 mm but $<$ 15 mm) should be considered non-target lesions. Nodes that have a short axis $<$ 10 mm are considered non-pathological and should not be recorded or followed.

A *sum of the diameters* (longest for non-nodal lesions, short axis for nodal lesions) for all target lesions will be calculated and reported as the *baseline sum diameters*. If lymph nodes are to be included in the sum, then as noted above, only the short axis is added into the sum. The baseline sum diameters will be used as reference to further characterize any objective tumor regression in the measurable dimension of the disease.

All other lesions (or sites of disease) including pathological lymph nodes should be identified as non-target lesions and should also be recorded at baseline. Measurements are not required and these lesions should be followed as ‘present’, ‘absent’, or in rare cases ‘unequivocal progression’ (see also Section 2.3.4).

In addition, it is possible to record multiple non-target lesions involving the same organ as a single item on the case report form (e.g. ‘multiple enlarged pelvic lymph nodes’ or ‘multiple liver metastases’).

2.3 RESPONSE CRITERIA

This section provides the definitions of the criteria used to determine objective tumor response for target lesions.

2.3.1 EVALUATION OF TARGET LESIONS

Complete Response (CR): Disappearance of all target lesions. Any pathological lymph nodes (whether target or non-target) must have reduction in short axis to $<$ 10 mm.

Partial Response (PR): At least a 30% decrease in the sum of diameters of target lesions, taking as reference the baseline sum diameters.

Progressive Disease (PD): At least a 20% increase in the sum of diameters of target lesions, taking as reference the smallest sum on study including baseline (nadir). In addition to the relative increase of 20%, the sum must also demonstrate an absolute increase of at least 5 mm. (Note: the appearance of one or more new lesions is also considered progression).

Stable Disease (SD): Neither sufficient shrinkage to qualify for PR nor sufficient increase to qualify for PD.

2.3.2 SPECIAL NOTES ON THE ASSESSMENT OF TARGET LESIONS

Lymph nodes: Lymph nodes identified as target lesions should always have the actual short axis measurement recorded (measured in the same anatomical plane as the baseline examination), even if the nodes regress to below 10 mm on study. This means that when lymph nodes are included as target lesions, the ‘sum’ of lesions may not be zero even if complete response criteria are met, since a normal lymph node is defined as having a short axis of $<$ 10 mm.

Target lesions that become ‘too small to measure’: while on study, all lesions (nodal and non-nodal) recorded at baseline should have their actual measurements recorded at each

subsequent evaluation, even when very small (e.g. 2 mm). However, sometimes lesions or lymph nodes which are recorded as target lesions at baseline become so faint on CT scan that the radiologist may not feel comfortable assigning an exact measure and may report them as being ‘too small to measure’. When this occurs it is important that a value be recorded on the case report form:

If it is the opinion of the radiologist that the lesion has likely disappeared, the measurement should be recorded as 0 mm.

If the lesion is believed to be present and is faintly seen but too small to measure, a default value of 5 mm should be assigned and BML (below measurable limit) should be ticked (Note: It is less likely that this rule will be used for lymph nodes since they usually have a definable size when normal and are frequently surrounded by fat such as in the retroperitoneum; however, if a lymph node is believed to be present and is faintly seen but too small to measure, a default value of 5 mm should be assigned in this circumstance as well and BML should also be ticked).

To reiterate, however, if the radiologist is able to provide an actual measure, that should be recorded, even if it is below 5 mm and in that case BML should not be ticked (BML is equivalent to a less than sign <).

Lesions that split or coalesce on treatment: when non-nodal lesions ‘fragment’, the longest diameters of the fragmented portions should be added together to calculate the target lesion sum. Similarly, as lesions coalesce, a plane between them may be maintained that would aid in obtaining maximal diameter measurements of each individual lesion. If the lesions have truly coalesced such that they are no longer separable, the vector of the longest diameter in this instance should be the maximal longest diameter for the ‘coalesced lesion’.

2.3.3 EVALUATION OF NON-TARGET LESIONS

This section provides the definitions of the criteria used to determine the tumor response for the group of non-target lesions. While some non-target lesions may actually be measurable, they need not be measured and instead should be assessed only qualitatively at the time points specified in the protocol.

Complete Response (CR): Disappearance of all non-target lesions (and, if applicable, normalization of tumor marker level). All lymph nodes must be non-pathological in size (<10 mm short axis).

Non-CR/Non-PD: Persistence of one or more non-target lesion(s) and/or maintenance of tumor marker level above the normal limits.

Progressive Disease (PD): Unequivocal progression (see Section 2.3.4) of existing non-target lesions. The appearance of one or more new lesions is also considered progression.

2.3.4 SPECIAL NOTES ON ASSESSMENT OF PROGRESSION OF NON-TARGET DISEASE

When the patient also has measurable disease: in this setting, to achieve ‘unequivocal progression’ on the basis of the non-target disease, there must be an overall level of substantial worsening in non-target disease in a magnitude that, even in presence of SD or PR in target disease, the overall tumor burden has increased sufficiently to merit discontinuation of therapy. A modest ‘increase’ in the size of one or more non-target lesions is usually not sufficient to qualify for **unequivocal progression** status. The designation of overall

progression solely on the basis of change in non-target disease in the face of SD or PR of target disease will therefore be extremely rare.

When the patient has only non-measurable disease: this circumstance arises in some phase III trials when it is not a criterion of study entry to have measurable disease. The same general concepts apply here as noted above, however, in this instance there is no measurable disease assessment to factor into the interpretation of an increase in non-measurable disease burden. Because worsening in non-target disease cannot be easily quantified (by definition: if all lesions are truly non-measurable) a useful test that can be applied when assessing patients for unequivocal progression is to consider if the increase in overall disease burden based on the change in non-measurable disease is comparable in magnitude to the increase that would be required to declare PD for measurable disease: i.e. an increase in tumor burden representing an additional 73% increase in ‘volume’ (which is equivalent to a 20% increase diameter in a measurable lesion). Examples include an increase in a pleural effusion from ‘trace’ to ‘large’, an increase in lymphangitic disease from localized to widespread, or may be described in protocols as ‘**sufficient to require a change in therapy**’. If ‘unequivocal progression’ is seen, the patient should be considered to have had overall PD at that point. While it would be ideal to have objective criteria to apply to non-measurable disease, the very nature of that disease makes it impossible to do so; therefore the increase must be **substantial**.

2.3.5 NEW LESIONS

The appearance of new malignant lesions denotes disease progression; therefore, some comments on detection of new lesions are important. There are no specific criteria for the identification of new radiographic lesions; however, the finding of a new lesion should be unequivocal: i.e. not attributable to differences in scanning technique, change in imaging modality or findings thought to represent something other than tumor (for example, some ‘new’ bone lesions may be simply healing or flare of pre-existing lesions). This is particularly important when the patient’s baseline lesions show partial or complete response. For example, necrosis of a liver lesion may be reported on a CT scan report as a ‘new’ cystic lesion, which it is not.

A lesion identified during the study in an anatomical location that was not scanned at baseline is considered a new lesion and will indicate disease progression.

If a new lesion is equivocal, for example because of its small size, continued therapy and follow-up evaluation will clarify if it represents truly new disease. If repeat scans confirm there is definitely a new lesion, then progression should be declared using the date of the initial scan.

2.4 EVALUATION OF RESPONSE

2.4.1 TIME POINT RESPONSE (OVERALL RESPONSE)

It is assumed that at each protocol specified time point, a response assessment occurs. Table A provides a summary of the overall response status calculation at each time point for patients who have measurable disease at baseline.

When patients have non-measurable (therefore non-target) disease only, Table B is to be used.

Table A Time Point Response – Target (w/wo non- target) Lesions

Target lesions	Non-target lesions	New lesions	Overall response
CR	CR	No	CR
CR	Non-CR/non-PD	No	PR
CR	Not evaluated	No	PR
PR	Non-PD or not all evaluated	No	PR
SD	Non-PD or not all evaluated	No	SD
Not all evaluated	Non-PD	No	NE
PD	Any	Yes or No	PD
Any	PD	Yes or No	PD
Any	Any	Yes	PD

CR = complete response, PR = partial response, SD = stable disease, PD = progressive disease, and NE = inevaluable.

Table B Time Point Response – Non-Target Lesions only

Non-target lesions	New lesions	Overall response
CR	No	CR
Non-CR/non-PD	No	Non-CR/non-PD ^a
Not all evaluated	No	NE
Unequivocal PD	Yes or No	PD
Any	Yes	PD

CR = complete response, PD = progressive disease, and NE = inevaluable.
a 'Non-CR/non-PD' is preferred over 'stable disease' for non-target disease since SD is increasingly used as endpoint for assessment of efficacy in some trials so to assign this category when no lesions can be measured is not advised.

2.4.2 MISSING ASSESSMENTS AND NOT-EVALUABLE DESIGNATION

When no imaging/measurement is done at all at a particular time point, the patient is not evaluable at that time point. If only a subset of lesion measurements are made at an assessment, usually the case is also considered not evaluable at that time point, unless a convincing argument can be made that the contribution of the individual missing lesion(s) would not change the assigned time point response. This would be most likely to happen in the case of PD.

For example, if a patient had a baseline sum of 50 mm with three measured lesions and during study only two lesions were assessed, but those gave a sum of 80 mm, the patient will have achieved PD status, regardless of the contribution of the missing lesion.

If one or more target lesions were not assessed either because the scan was not done, or could not be assessed because of poor image quality or obstructed view, the Response for Target

Lesions should be “Unable to Assess” since the patient is not evaluable. Similarly, if one or more non-target lesions are indicated as ‘not assessed’, the response for non-target lesions should be “Unable to Assess” (except where there is clear progression). Overall response would be “Unable to Assess” if either the target response or the non-target response is “Unable to Assess” (except where this is clear evidence of progression) as this equates with the case being not evaluable at that time point.

Table C Best Overall Response when Confirmation is required

Overall response First time point	Overall response Subsequent time point	BEST overall response
CR	CR	CR
CR	PR	SD, PD or PR ^a
CR	SD	SD provided minimum criteria for SD duration met, otherwise, PD
CR	PD	SD provided minimum criteria for SD duration met, otherwise, PD
CR	NE	SD provided minimum criteria for SD duration met, otherwise NE
PR	CR	PR
PR	PR	PR
PR	SD	SD
PR	PD	SD provided minimum criteria for SD duration met, otherwise, PD
PR	NE	SD provided minimum criteria for SD duration met, otherwise NE
NE	NE	NE

CR = complete response, PR = partial response, SD = stable disease, PD = progressive disease, and NE = inevaluable.
^a If a CR is truly met at first time point, then any disease seen at a subsequent time point, even disease meeting PR criteria relative to baseline, makes the disease PD at that point (since disease must have reappeared after CR). Best response would depend on whether minimum duration for SD was met. However, sometimes ‘CR’ may be claimed when subsequent scans suggest small lesions were likely still present and in fact the patient had PR, not CR at the first time point. Under these circumstances, the original CR should be changed to PR and the best response is PR.

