5.3.6 Response Criteria

5.3.6.1 Solid tumours

Response of measurable solid tumours to study treatment will be evaluated by the Investigator according to RECIST, v1.1 criteria ([Appendix 4](#)) (67). See [Appendix 9](#) for prostate, [Appendix 10](#) for ECD and/or LCH specific response criteria.

Tumour evaluations will occur once during the Screening Period (Days –28 and –1), every 8 weeks after starting vemurafenib during the Treatment Period, and at the End of Treatment Visit. A window of \pm 5 days of scheduled visit is allowed to complete the tumour assessments at the required intervals.

Radiological tumour assessments to measure extent of disease will be carried out by CT/MRI of the chest/abdomen/pelvis (C/A/P) for all patients. In addition, CT/MRI of the brain can be performed if clinically indicated and as per standard care.

Patients should be assessed at the designated time points using a consistent imaging modality. The same imaging technique must be used for a patient throughout the study. The same method of assessment and the same technique should be used to characterize each identified and reported lesion at baseline and during follow-up. If more than one method of assessment is used at baseline, the most accurate method according to RECIST should be selected when recording data; in addition, this method should be performed in all subsequent evaluations. Tumour measurements should be made by the same Investigator/radiologist for each patient during the study to the extent that this is feasible.

For solid tumours to be assigned a status of partial response (PR) or complete response (CR) (i.e., a responder), changes in tumour measurements must be confirmed by repeat assessments performed no less than 4 weeks after the criteria for response are first met, i.e., patients need to have two consecutive assessments of PR or CR to be a responder.

Symptomatic deterioration may indicate progressive disease (PD). However, radiological confirmation of PD is strongly recommended.

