8. STATISTICAL CONSIDERATIONS AND ANALYTICAL PLAN

8.1 PRIMARY AND SECONDARY STUDY VARIABLES

8.1.1 Primary Variable

Response rate at Week 8, as assessed by the Investigator using RECIST, v1.1* for patients with solid tumours or IMWG uniform response criteria for patients with MM, is the primary endpoint for each cohort. For patients with solid tumours, responders at Week 8 will be defined based on tumour assessment status of PR or CR at Week 8. For patients with MM, responders at Week 8 will be defined based on tumour assessment status of CR, sCR, VGPR or PR. Only patients with measurable disease at baseline will be included in the analysis of the RR. Patients without a post-baseline tumour assessment will be considered to be non-responders.

There will be 7 cohorts with different cancer types. There will be Cohort 3a and 3b with patients with colorectal cancer treated with vemurafenib or vemurafenib in combination with cetuximab, respectively.

Cohort 3b has two parts,

Part 1 is a dose finding phase for vemurafenib in combination with cetuximab (based on a classical 3+3 design)

Part 2 is investigating the efficacy and safety of the recommended dose for stage I/II of the combination of vemurafenib and cetuximab

*see [Appendix 9](#) for prostate cancer, [Appendix 10](#) for ECD and/or LCH response criteria

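### Appendix 4 gives two overall responses when target lesions are evaluated but a non-target lesion is not (Table A: PR or SD; 2.4.2: not evaluable), so Week 8 responder status depends on which rule is used

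*Protocol*

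**What the plan says.** Section 5.3.6.1 sends the reader to Appendix 4: "Response of measurable solid tumours to study treatment will be evaluated by the Investigator according to RECIST, v1.1 criteria". Section 8.1.1 then fixes the primary endpoint for solid tumours: "responders at Week 8 will be defined based on tumour assessment status of PR or CR at Week 8".

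Appendix 4 contains two rules for a scan on which some non-target disease was not assessed.

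- **Section 2.4.1, Table A** (patients with measurable disease at baseline). With no new lesion, target PR and non-target "Non-PD or not all evaluated" gives overall PR. The same non-target entry with target SD gives SD. Target CR with non-target disease not evaluated gives PR.
- **Section 2.4.2.** A first rule applies "if one or more non-target lesions are indicated as" missing at that visit: the non-target component becomes *Unable to Assess*, unless progression is evident. A second rule gives the overall response that same label "if either the target response or the non-target response is" so classed, with the same exception. The section explains that such a patient counts as not evaluable at that visit.

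Table B covers patients with non-target disease only. There, non-target lesions not all evaluated, with no new lesion, give NE.

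**The concern.** Both rules apply to the same scan: target lesions measured, at least one non-target lesion not assessed, no new lesion, no progression. They return different overall responses, and no section gives an order of precedence.

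The choice reaches the Week 8 response rate in the solid-tumour cohorts and the Stage I count out of seven. Through the SD row it reaches the clinical benefit rate. Through Table C, where PR followed by NE is at best SD, it reaches confirmed BOR. Multiple myeloma is unaffected because it uses IMWG criteria. Unassessed target lesions are also unaffected, because Table A and 2.4.2 agree there.

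**Working it through.** **1. The same scan under each rule** (no new lesion, no progression, one or more non-target lesions not assessed)

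| Target response | Table A | Section 2.4.2 | Week 8 responder (Table A / 2.4.2) |
|---|---|---|---|
| CR | PR | Unable to Assess | yes / no |
| PR | PR | Unable to Assess | yes / no |
| SD | SD | Unable to Assess | no / no (clinical benefit rate affected) |

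**2. Why the 2.4.2 outcome counts as a non-response.** The missing-data sentence in 8.1.1 names only patients with no post-baseline assessment, so it does not decide this case. A patient rated *Unable to Assess* still lacks PR or CR. The main efficacy population in 8.2 is intent-to-treat. Section 8.1.1 restricts the response-rate analysis to patients with measurable disease at baseline, and a patient with target lesions meets that restriction. The patient therefore stays in the denominator as a non-responder.

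**3. The plan's own operating characteristics.** Inputs are from 8.3.1.1 and Table 16: 7 patients in Stage I; 2–4 responders lead to 19 patients with at least 5 responders needed; 5 or more lead to 13 patients with at least 6 needed. Write b(n, x, p) for the binomial probability. Then

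P(p) = Σ(x=2..4) b(7,x,p)·Pr[Bin(12,p) ≥ 5−x] + Σ(x=5..7) b(7,x,p)·Pr[Bin(6,p) ≥ 6−x]

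- p = 0.15: 0.0998 (stated alpha 10%)
- p = 0.35: 0.6532 + 0.0521 = 0.7053 (stated power 70%)
- p = 0.45: 0.733 + 0.1497 = 0.883 (stated power 80%)

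The enumeration agrees with the stated 10% and 70%, and the stated 80% is at least met.

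**4. Cohorts sitting where one patient decides**

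- Stage I, exactly 2/7: b(7, 2, 0.35) = 21 × 0.35² × 0.65⁵ = 0.298. At 15% it is 0.210 and at 45% it is 0.214.
- Stage II, low branch, exactly 5/19 at 35%: Σ(x=2..4) b(7,x)·b(12,5−x) = 0.093.

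These are the probabilities of standing on the boundary. They are not the probability that a patient there is affected.

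**5. Illustration with an assumed share.** Suppose a share q of true responders has an unassessed non-target lesion at Week 8 and 2.4.2 is always applied. The effective rate is then p(1−q). The documents give no q. At a true 35%:

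| q (assumed) | Effective rate | Pass Stage I on count | Meet Table 16 count |
|---|---|---|---|
| 0 | 0.350 | 0.766 | 0.705 |
| 5% | 0.3325 | 0.735 | 0.661 |
| 10% | 0.315 | 0.701 | 0.612 |
| 20% | 0.280 | 0.627 | 0.503 |

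Under Table A the figures stay at 0.766 and 0.705 for every q.

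**6. The other Stage II route.** Section 8.3.1.2 also accepts a cohort if confirmed BOR is above 15%. Since 4/19 = 21.1% and 3/19 = 15.8%, a cohort that drops to 4/19 on the count can still qualify if enough responses are confirmed.

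**The case against.** The strongest textual defence is that 2.4.2 already leaves room for judgement. A partly measured scan is only usually not evaluable, "unless a convincing argument can be made that the contribution of the individual missing lesion(s) would not change the assigned time point response". That clause qualifies an earlier sentence and is discretionary. The later sentence on overall response excepts only clear progression. Table A, for its part, cannot be read as covering complete scans only, because its rows name unevaluated non-target disease. The conflict remains.

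The second defence is rarity. CT or MRI of chest, abdomen and pelvis is required every 8 weeks (primary brain tumours excepted), so missing non-target disease in those regions would usually mean a missed mandatory scan. This limits the size and makes a 20% share an extreme case. It does not remove the trigger. Some patients with asymptomatic brain metastases are eligible under 4.3, while brain imaging follows standard care. A non-target brain lesion can therefore go unassessed without any departure from the schedule.

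Three stronger readings are tempting, and the documents do not support them:

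- *One reclassified patient reverses the Stage II conclusion.* It can reverse the Table 16 count, but the confirmed-BOR criterion is an alternative. BOR also runs until progression or death, so a patient not evaluable at Week 8 may still become a confirmed responder later.
- *The trial loses a known amount of power.* The shares are assumed, and the series measures only the chance of meeting the Table 16 count.
- *Investigator and IRC will disagree because of this.* That would require the two to apply different rules, and the protocol does not show which rule the IRC uses.

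At Stage I, falling below 2/7 does not always close a cohort, because Stage II entry may be allowed for clear clinical benefit. That exception is discretionary, and its example assumes no CR or PR, so it does not squarely cover 1/7.

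**Conclusion.** The inconsistency stands in the current text and reaches the primary endpoint. For a patient with target CR or PR and an unassessed non-target lesion, Table A yields a responder and 2.4.2 a non-responder. The two results are response versus not evaluable, rather than response versus progression, but the split on the primary endpoint is exact.

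The firmest consequence is at Stage I, where a single such patient separates continuing from stopping on the count in a cohort standing at 2/7. At Stage II the effect is confined to the responder-count criterion. The fall in step 5 shows direction and sensitivity only, since it assumes both the share affected and uniform use of 2.4.2.

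A reader might also infer that Table A is right and 2.4.2 an error. The protocol does not establish that. Either rule could be adopted, provided one is stated.

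**What to change.** State one rule for unassessed non-target lesions in patients who have target disease, and align Table A and 2.4.2 with it. The simplest route keeps Table A:

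- For patients with measurable disease at baseline, overall response follows Table A. Target CR with unevaluated non-target disease is then capped at PR, as the table already provides.
- Amend the overall-response sentence in 2.4.2 so that a non-target *Unable to Assess* makes the overall response not evaluable only in patients with non-target disease alone. This keeps it consistent with Table B. It matters because Appendices 9 and 10 admit prostate and ECD/LCH patients with non-measurable disease, so the carry-over cannot simply be limited to target lesions.
- Leave the target-lesion carry-over and the clear-progression exception unchanged.
- Apply the same rule to the investigator and IRC derivations.

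The cost is an amended sentence in Appendix 4 with matching derivation rules for the eCRF and the IRC. No additional scans or data are needed.
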